Nordic Naturals adheres to high standards on safety and purity by setting low levels of allowances for peroxides, heavy metals, dioxins, furans, and PCBs. A certificate of analysis is provided for every batch of ProDHA based on both an internal analysis and an analysis conducted by an independent laboratory.

The investigational pharmacy at the University of Chicago will use computer generated random assignment of ID numbers to active supplement or placebo in blocks of 18: 12 ID numbers will be randomized to active supplement and six to placebo. In order to maintain the double-blind, the pharmacist will divide each randomization block of 18 ID numbers into groups of three: six ID numbers were assigned to group A (placebo) and the remaining 12 will be assigned to either group B or C, both of which will receive identical doses of active supplement. This approach will allow the pharmacist to randomize on a 2:1 ratio without having the unbalanced design break the blind. Once the study is complete and the blind broken, the two groups receiving identical doses of active supplement will be combined for analyses.

Each participant will receive a 6-week supply. She will bring any unused DHA back to her next visit; pills will be double counted at that time as an additional method for monitoring compliance. At each visit she will receive the next supply. Research assistants will contact participants by phone 3 times per week to ask the time of day that supplement was taken, and data on perception of taste, and possible gastrointestinal side effects. At each laboratory visit research assistants will interview participants about diet over the past 24 hours and past two weeks to determine intake of sea fish or other DHA rich foods (e.g., flax seed).

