Response to a controlled stressor including cortisol, blood pressure, and heart rate will be better modulated among women receiving DHA supplementation than among women who do not, as demonstrated by a lower peak response and more rapid recovery to baseline. Differences in stress reactivity (i.e., cortisol levels, blood pressure, and heart rate) will be tested using two complementary approaches. First, we will use rmANOVA with supplement group as the between-subjects factor and timing of measurement (e.g. 20 minutes and 5 minutes pre-TSST, and 20, 40, and 50 minutes post-TSST for cortisol) as the within-subjects factor for each of the 4 prenatal visits separately. The interaction between group and time will be tested. For further interrogation of these changes, a random intercept, random slope mixed-effects model will be fit and results compared to the rmANOVA results. Second, the area under the curve (AUC) will be calculated for each participant at

each visit. Since primary interest is in assessment of changes over time, the AUC_I (area under the curve with respect to increase) will be used (Pruessner et al., 2003). Differences in these AUCs will be tested using rmANOVA with supplement group as the between-subjects factor and visit as the within-subjects factor. The interaction between group and visit will also be included to explore whether the magnitude of the difference between the groups is affected by the length of DHA supplementation. A Greenhouse-Geisser sphericity adjustment will be employed in both rmANOVA analyses. For further exploration of the patterns over time, a cluster analysis using the AUCs at each visit will be performed, and the association between the "change groups" formed from this cluster analysis and supplement group will be determined using a chi-square or Fisher's exact test. Log-transformed cortisol values will be used if appropriate. Also, time of collection and prenatal depression and anxiety will be controlled for in these analyses if needed.

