Power Calculations for Hypothesis 1. In this study with 108 participants in the supplement group and 54 in the placebo group, there will be >90% power to detect a difference in stress levels, at any particular visit, of the same magnitude as that observed in our preliminary study at 30 weeks (27.5+/-3.4 vs. 29.3+/-3.1), using a two-sided test at the 0.05 significance level. Additionally, with 162 participants, there will be 80% power to detect a correlation of 0.22 between changes in DHA levels in the blood versus changes in perceived stress. For the cortisol response to the TSST, there will be >95% power to detect a difference in AUCs at a given visit of the same magnitude as that found in our preliminary study at 30 weeks (-4.5+/-3.9 vs. -8.1+/-6.1; negative values indicating net decreases rather than increases), using a two-sided test at the 0.05 significance level.

Hypothesis 2. DHA supplementation during pregnancy will improve infant birth and developmental outcomes among African American women living in urban poverty.

Infants of mothers who receive DHA supplementation will have longer gestations, higher birth weights, more optimal neurodevelopmental outcomes as measured by the NBAS and Bayley Scales of Infant Development, and more optimal maternal reports of temperament in comparison to infants whose mothers did not receive DHA supplementation. We will use ANOVA (e.g. birth weight) or rmANOVA (e.g. NBAS) to test for significant differences between treatment groups. For categorical infant outcomes, such as pre-term birth or low Apgar scores, logistic regression will be employed. We will also test the association between level of DHA in blood at the last prenatal visit and/or change in DHA levels from baseline and infant outcomes using linear (e.g. birth weight or change in NBAS) or logistic (e.g. pre-term birth) regression.

Transformations of the continuous dependent measures will be performed to stabilize the variance across groups if needed.

Infants of mothers who received DHA supplements will demonstrate more modulated cortisol response to the NBAS and still-face paradigm, with a lower peak response and a steeper slope from peak to recovery, in comparison to infants whose mothers did not receive DHA supplementation. Analyses will be performed as described for Hypothesis 1.

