Infant gender, mothers' postpartum stress, depression, and anxiety levels will be compared between those received DHA supplements during pregnancy and those who did not using ANOVA. If significant differences are found, then these factors will also be controlled for in the analyses. If time of collection is associated with cortisol values, then this will also be controlled for in the analyses. However, since a circadian rhythm is not firmly established prior to the age of 6 months, we do not expect to have to control for time of day at 1 and 4 months.

Power Calculations for Hypothesis 2. Based on published data on maternal report of difficult temperament in infants using the ICQ (Keenan et al., 1998), the estimated SD for the ICQ in the proposed study is 7.8. With 108 participants in the supplement group and 54 in the placebo group, there will be 80% power to detect a difference in the ICQ of 3.7 between the two groups at a given visit, using a two-sided test at the 0.05 significance level.

The SD for 30–minute post-test cortisol levels in response to the FFSF paradigm was reported as 0.4 μ g/dL (Hayley & Stansbury, 2003). If we assume a similar amount of variability in peak responses to the FFSF, with 108 participants in the supplement group and 54 in the placebo group, there will be 80% power to detect a difference of 0.19 μ g/dL between the two groups, using a two-sided test at the 0.05 significance level.

[figure not shown]
In addition, there will be approximately 90% power to detect a difference in birth weights of the same magnitude as that observed in our preliminary study (3174+/-480 vs. 2889+/-549 g), using a two-sided test at the 0.05 significance level.

Hypothesis 3. The association between DHA supplementation during pregnancy and infant outcomes will be partially mediated by reductions in maternal perceived stress, stress reactivity during pregnancy.

Mediation will be tested using the Baron and Kenny approach (Baron & Kenny, 1986) with the following general model:

$$g(E(Y_i)) = \alpha + \beta M_i + \omega T_i + \lambda Z_i$$

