 Y_i is an outcome for infant i, g is a link function (e.g. logistic or identity), M_i is a maternal stress measure at the final prenatal visit for the mother of infant i, T_i is treatment group (e.g. 0=placebo vs. 1=active; average DHA level in the blood across prenatal visits), and Z_i is a vector of additional covariates such as infant gender, mothers' postpartum stress, depression, or anxiety. The change in ω due to adding maternal stress to the model provides an estimate of the proportion of the treatment effect due to this factor; if ω is still significant but the magnitude is reduced, this would provide evidence for partial mediation. For infant outcomes collected at multiple visits, the initial approach will be to use data from the last visit, but longitudinal approaches may be considered depending on the results from the initial analyses. To provide greater power for detecting such effects, bootstrapped confidence intervals will be examined. Since multiple measures of maternal stress will be collected, the model may be extended to permit multiple mediators.

Power Calculations for Hypothesis 3. Based on simulation results presented in Fritz et al. and the SAS program provided at http://ripl.faculty.asu.edu/wp-content/uploads/2013/02/baronkenny3.txt, 162 subjects will provide sufficient power (>80%) to detect the following effects based on Cohen's criteria. As shown in Figure 6 and Table 2, the study with 162 subjects will be sufficiently powered (>80%) to detect medium effects for the α and β paths and small effects for the direct effect (scenario 1), or small-medium effects for the α and β paths and medium effects for the direct effect (scenario 2), which is plausible based on the effects found in the preliminary study.

Table 2: Overview of power for mediation hypothesis

	α path	β path	Direct effect	
scenario 1	medium	medium	small	
scenario 2	small-medium	small-medium	medium	

Missing data. Missing data is not expected to be a major issue based on retention rates from the preliminary study. The last observation carried forward (LOCF) approach for missing data will be employed. Sensitivity analyses using complete-cases only will also be performed and the results using the two approaches compared. Related to this, treatment non-compliers will be included in the primary analysis based on the intent-to-treat (ITT) principle.

Timeline for participant visits

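### In the Hypothesis 2 group comparisons infant sex is adjusted for only if the arms differ significantly on it, and no pre-randomisation covariate is pre-specified, so available precision is forgone

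*Combined protocol and SAP*

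**What the plan says.** The group comparison for infant outcomes is given under Hypothesis 2: "We will use ANOVA (e.g. birth weight) or rmANOVA (e.g. NBAS) to test for significant differences between treatment groups". For binary outcomes, "For categorical infant outcomes, such as pre-term birth or low Apgar scores, logistic regression will be employed". Neither sentence names a covariate.

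Covariates come in a later paragraph of the same section. Infant sex and three maternal scores taken after birth (stress, depression, anxiety) are to be tested between the arms by analysis of variance. The rule that follows is: "If significant differences are found, then these factors will also be controlled for in the analyses". The significance level for this screen is not stated.

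Three other places bear on the point:

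- **Infant cortisol (Hypothesis 2).** "Analyses will be performed as described for Hypothesis 1". Hypothesis 1 in turn allows that "time of collection and prenatal depression and anxiety will be controlled for in these analyses if needed". This clause is conditional and does not say which prenatal visit is meant.
- **Mediation model (Hypothesis 3).** The covariate term is described as "a vector of additional covariates such as infant gender, mothers' postpartum stress, depression, or anxiety", with no significance condition.
- **Randomisation (Nutritional Supplement).** Assignment is "in blocks of 18: 12 ID numbers will be randomized to active supplement and six to placebo". No stratification factor is stated.

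**The concern.** Infant sex is fixed before the mother is randomised, so any difference between arms on it arises by chance. Testing that difference asks a question whose answer is already known. It does not address the useful question, which is whether sex predicts the outcome. The plan uses the better criterion elsewhere: under Hypothesis 2, time of collection enters the cortisol models if it is associated with cortisol. As written, Hypothesis 2 could leave sex out while Hypothesis 3 adjusts the same infant outcome for it.

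The maternal scores at the first visit are the more valuable omission. The Infant outcomes section says the measures were chosen partly because they are linked to maternal stress in pregnancy, and it names temperament as an example. Perceived stress, depression and anxiety questionnaires are part of every prenatal visit. In Figure 5 they fall in the same closing block as supplement distribution, so first-visit scores precede supplementation. None of them is pre-specified for the Hypothesis 2 comparisons.

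At stake are the precision of the infant comparisons, two of which are planned at only 80% power, and chance imbalances left in the estimates.

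**Working it through.** **Inputs from the plan.** 108 vs 54 analysed, two-sided 0.05; ICQ SD 7.8 and difference 3.7 at 80% power; birth weight 3174 (SD 480) vs 2889 (SD 549) g at approximately 90% power (all from Power Calculations for Hypothesis 2).

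**Assumptions, not in the documents.** Screen at 0.05; about 50% boys; sex difference in birth weight of 80–160 g; R² of 0.01–0.02 for sex and 0.05–0.16 for baseline maternal scores on the ICQ.

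**1. The plan's own figures.** √(1/108 + 1/54) = 0.1667. For the ICQ, the standard error is 7.8 × 0.1667 = 1.30 and 3.7/1.30 = 2.85. Power is 80.8% by noncentral t (81.2% by the normal approximation), against the stated 80%. For birth weight, the pooled SD is √[(107 × 480² + 53 × 549²)/160] = 504 g, the standard error is 84 g, and power for 285 g is 92% (89.5% with unequal variances), against approximately 90%. Both reproduce.

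**2. When the sex screen fires.** The SE of the difference in proportion of boys is 0.5 × 0.1667 = 0.083. The trigger is 1.96 × 0.083 = 0.163, about 16 percentage points. As a check, 50% vs 64.8% boys gives p = 0.075 (not adjusted) and 50% vs 66.7% gives p = 0.045 (adjusted). An imbalance above 10 points has probability about 23%. Since only about 5% of trials exceed the trigger, most of those would stay unadjusted.

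**3. What an unadjusted sex imbalance does to birth weight.**

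| Imbalance | Shift at 80 g | Shift at 160 g | Share of the 84 g SE |
|---|---|---|---|
| Expected absolute value, 0.083 × √(2/π) = 6.6 points | 5 g | 11 g | 0.06–0.13 |
| Just below the trigger, 16.3 points | 13 g | 26 g | 0.16–0.31 |

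The second row is a ceiling: 5–9% of the 285 g target.

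**4. What always adjusting gains on the ICQ.** Residual SD = 7.8 × √(1 − R²), noncentral t:

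| R² (assumed) | Residual SD | Power for 3.7 | Difference detectable at 80% |
|---|---|---|---|
| 0 | 7.80 | 80.8% | 3.66 |
| 0.01 | 7.76 | 81.2% | 3.65 |
| 0.02 | 7.72 | 81.5% | 3.63 |
| 0.05 | 7.60 | 82.7% | 3.57 |
| 0.09 | 7.44 | 84.3% | 3.50 |
| 0.16 | 7.15 | 87.0% | 3.36 |

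Sex alone (rows 0.01–0.02) adds under 1 point. For R² of 0.05–0.16 the gain equals about 9–31 extra participants, from 162 × R²/(1 − R²).

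**5. What a significance screen recovers.** Simulation of one continuous covariate, 6,000 runs per setting, true difference 3.7/7.8 SD:

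| R² | Unadjusted | Adjust only if arms differ | Always adjust |
|---|---|---|---|
| 0.09 | 81.3% | 81.8% | 85.2% |
| 0.20 | 80.4% | 81.4% | 88.5% |

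With no true difference, rejection under the screen was 0.041–0.054 across the settings run, so type I error is not inflated.

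**The case against.** The strongest case against is that nothing here is invalid. Randomisation justifies the unadjusted comparison, its standard error already allows for chance imbalance, and the plan meets its stated power without covariates. That stands. A reader might infer that the screen biases the infant results or inflates false positives; neither the design nor the simulation supports that.

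A reader might also infer that no baseline variable can enter any infant analysis. The documents do not support this. The infant cortisol analyses inherit the conditional clause on prenatal depression and anxiety, and the mediation model lists infant sex among its example covariates. The supportable statement is narrower: nothing is pre-specified in the Hypothesis 2 group comparisons.

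The quoted rule is also not the source of the larger gain. Baseline maternal scores were never subject to the screen; they are simply not in the models. Removing the screen for sex alone changes little, and the 13–26 g is the most that can escape it, not a typical shift. The size of the larger gain rests on an R² that the documents do not give.

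Finally, body mass index appears only as an eligibility item, and Table 1 lists gestational age only as a birth outcome. It should not be taken for granted that either is recorded as an enrolment value for analysis.

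These objections limit the size and wording of the point. They do not defend selecting a covariate by a test of arm differences.

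**Conclusion.** The point holds for the Hypothesis 2 group comparisons, as an inefficiency that costs almost nothing to remove. Selecting infant sex by a test between randomised arms adds it in about 1 trial in 20 (0.05 assumed) and leaves nearly all the available precision unused. Sex itself matters little: under 1 percentage point of power, and a typical birth-weight shift of 5–11 g against a standard error of 84 g, if the sex difference is 80–160 g. Baseline maternal scores matter more: ICQ power rises from 81% to 83–87% if they explain 5–16% of the variance, with only about 2 points gained at the low end. The harm is forgone precision and uncorrected chance imbalance, not bias or loss of type I error control. It should be changed before analysis but does not threaten the trial's conclusions. The postpartum maternal scores in the same sentence are measured after randomisation; they raise a separate question that is not assessed here.

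**What to change.** 1. Remove the significance screen for infant sex.
2. In the continuous Hypothesis 2 models, pre-specify infant sex and a short set of maternal scores from the baseline, pre-supplement visit (perceived stress, Edinburgh depression, Spielberger anxiety) as fixed covariates, whatever imbalance is observed.
3. For birth weight, pre-specify infant sex, plus gestational age at randomisation and baseline body mass index if these are recorded at enrolment.
4. Report the unadjusted comparison alongside as a check.

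The cost is SAP wording and a few degrees of freedom: about four of 160 for the ICQ model, which leaves the power figures above unchanged to the nearest 0.1 point. The maternal scores are already collected at the prenatal visits. The wording should be settled before the blind is broken.

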-20 -5 +20 +40 +50 saliva saliva saliva saliva saliva 2 3 5 Consent & Instrumentation BP (x4) BP (x1) BP (x1) BP (x1) BP (every 5 minutes) HR (x 4) HR (x 2) HR (x 2) HR (x 2) HR (every 5 minutes) Questionnaires, supplement distribution, **Baseline Prepare** Speech Math Snack **Blood Draw** scheduling (20 min) (3 min) (3 min) (3 min) (5 mins) (10 mins) (50 min)

Figure 5. Protocol for prenatal laboratory visits

Methods

All visits will take place in the Department of Psychiatry and Behavioral Neuroscience at the University of Chicago. All prenatal visits will follow the same protocol (see Figure 5). Participants will provide a saliva sample upon arrival to the laboratory and an occluding cuff will be placed on the non-dominant arm for automated measurement of BP. A 3-lead electrocardiogram (ECG) will be attached to the shoulders and xyphoid process for continual measurement of heart rate. Following instrumentation, there will be a period of acclimation during which they will rest quietly while viewing a non-stressful video at the end of which a second saliva sample will be obtained. This will be followed by administration of the Trier Social Stress Test (TSST). Participants will complete psychosocial stress questionnaires following the TSST. These questionnaires will cover perceived stress, stressful life events, and symptoms of anxiety and depression. Following the final saliva sample, participants will be provided with a snack and then will be accompanied to the Clinical Research Center (which is located two floors above our laboratory) for the blood draw which will be used to assess DHA levels and inflammatory markers (C-reactive protein (CRP); IL-6; TNF-α).

Offspring stress reactivity will be measured via behavioral and cortisol response to the Brazelton Neonatal Behavioral Assessment Scale (NBAS) at 1 month and in response to the Face-to-Face Still-Face (FFSF) paradigm at 4 and 9 months. Infant cognitive development and behavior and emotion regulation during developmental testing also will be assessed.

Nutritional Supplement. As in the pilot study, the nutritional supplement we propose to use is ProDHA. The same dose will be used, with 2 gel capsules providing: 450 mg of DHA; 40 mg of DPA and ETA; 90 mg EPA; and 15 IU Vitamin E.

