The *Bayley Scales of Infant Development* (Third Edition) (BSID-III; 2006) will be administered as an index of developmental functioning. The Bayley Behavior Ratings will be used to generate continuous scores for observed emotion and behavior regulation during testing. Temperament will be measured using The Infant Characteristics Questionnaire (ICQ; Bates, Freeland, & Lounsbury, 1979), which is designed specifically to assess regulation of negative emotion, and the Infant Behavior Questionnaire-Revised (IBQ-R; Gartstein & Rothbart, 2003), a broader measure of temperament. The ICQ contains 32 seven-point items that assess temperamental characteristics, including fussy-difficult and unadaptable characteristics. The instrument has been shown to have good criterion validity (Bates, Freeland & Lounsbury 1979), and has the additional advantage of being short, and easy to understand. The IBQ-R short form contains 36 items that load on three dimensions: Surgency/Extraversion, Negative Affectivity, and Orienting/Regulation, and has been shown to have adequate reliability and validity (Garstein & Rothbart, 2003)

Cortisol response to NBAS in the first month and to the *Face-to-Face Still-Face* (FFSF; Tronick et al., 1978) at 4 and 9 months will be used to measure stress reactivity. The FFSF is a standard laboratory procedure that is comprised of three 2-minute episodes: mother playing typically with her seated infant, followed by mother maintaining a neutral expression and no vocalization, followed by a return to typical play. The FFSF reliably produces physiological arousal in infants including increases in cortisol (Field, 1994; Hayley & Stansbury, 2003). Collection and assays of saliva samples will be conducted as described above for the mothers. Effects of time of day on the pattern of cortisol response will be tested,

and if necessary controlled for in the analyses. Infants will be required to have not consumed any milk products (human or animal) for 1 hour prior to and during saliva collection. Saliva will be collected at four time points: 5 and 0 minutes pre-FFSF, and 20 and 40 minutes post-FFSF by swabbing the infants' mouths with an unflavored dental roll.

An overview of the main study variables is provided in Table 1. We also will assess maternal weekly sea fish intake at the post-partum visits and type of infant formula to control for possible postnatal omega-3 intake by the infant.

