Measure	Variables		16-20 wks	24-30 wks	34-36 wks	1 month	4 months	9 months
Maternal Psychosocial Stress								
Perceived stress	Perceived stress Total score from PSS		1	>	>	>	>	1
Life events	Life events Total score from DLC		1	1	1	1	1	1
Depressed mood		1	1	1	1	1	1	1
Anxiety Total score from STAI		/	1	1	1	1	/	1
Maternal Stress Response								
Reactivity to TSST	Cortisol; HR, BP	>	1	>	>			
DHA Levels								
Blood draw	DHA levels in red blood cells	>	1	1	1			
Maternal Inflammatory Markers								
Blood draw	CRP; IL-6; TNF-α	>	1	>	>			
Infant Outcomes								
Birth	Birth weight, gestational age, Apgar, meconium					1		
Neurodevelopmental functioning	NBAS, BSID					1	1	1
Stress reactivity	Cortisol response to NBAS, FFSF					>	>	1
Temperament	IBQ; IBQ-R – short form						1	1

Table 1. Overview of main study variables

Hypotheses and Analyses

Hypothesis 1. DHA supplementation will improve maternal health during pregnancy among African American women living in urban poverty. Women who receive DHA supplementation will report lower levels of self-reported perceived stress over time, despite a lack of change in exposure to environmental stressors. Inflammatory markers including C-reactive protein (CRP), IL-6, TNF-α will be lower among women receiving DHA supplementation compared to placebo. To test for significant differences in perceived stress and inflammatory marker levels we will use repeated measures ANOVA (rmANOVA) with supplement group as the between-subjects factor and visit as a within-subjects factor. The interaction between group and time will be of particular interest. A Greenhouse-Geisser sphericity adjustment (Geisser & Greenhouse, 1958) will be employed. If any of the dependent measures exhibit a non-normal distribution (e.g. CRP), then a suitable data transformation will be used. Changes over time in prenatal levels of depression and anxiety will also be assessed using rmANOVA. Scatter plots and box plots of the data will be used to further explore these relationships. Plots of the data also will be examined to detect nonlinear time effects in addition to using orthogonal polynomial contrasts to formally test for quadratic and cubic effects. The association between change in DHA levels in the blood from baseline to the last prenatal visit and change in perceived stress will be examined using linear regression models.

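### If DHA lowers perceived stress, shared maternal reporting can make PSS appear to mediate mother-rated temperament, and the Hypothesis 3 model does not name the baseline PSS that would reduce this.

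*Combined protocol and SAP*

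**What the plan says.** All references are to the combined protocol and SAP.

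- **Mediator.** Under Hypothesis 3, "M_i is a maternal stress measure at the final prenatal visit for the mother of infant i". Perceived stress is one of the mediators named in the hypothesis. It is a self-report: under Hypothesis 1, "Women who receive DHA supplementation will report lower levels of self-reported perceived stress over time".
- **Outcome.** The model accepts any infant outcome. Hypothesis 2 includes "more optimal maternal reports of temperament in comparison to infants whose mothers did not receive DHA supplementation", and the infant outcomes section says "Temperament will be measured using The Infant Characteristics Questionnaire", together with the IBQ-R short form.
- **Covariates.** "Z_i is a vector of additional covariates such as infant gender, mothers' postpartum stress, depression, or anxiety". The list is open, and baseline PSS is not on it.
- **Decision rule.** The Baron and Kenny approach is used. The change in the treatment coefficient ω when stress is added is read as the proportion of effect due to stress, and "if ω is still significant but the magnitude is reduced, this would provide evidence for partial mediation". Bootstrapped intervals are also examined.
- **What is available.** For the prenatal laboratory visits, "All prenatal visits will follow the same protocol (see Figure 5", and that protocol includes the perceived-stress questionnaire. PSS is therefore collected at the baseline visit, where supplement is first handed out. Infant measures that do not come from the mother are also planned: NBAS, Bayley, infant cortisol, and the examiner's ratings ("The Bayley Behavior Ratings will be used to generate continuous scores for observed emotion and behavior regulation during testing").

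**The concern.** A mother who tends to answer questionnaires negatively will score high on her own PSS and will also rate her infant as more difficult. The two scores are then correlated even if prenatal stress has no effect on the infant. Random assignment makes this tendency independent of supplement group, so the supplement-to-PSS coefficient is unbiased. It does not make PSS independent of the tendency within groups, so the PSS-to-temperament coefficient (β) is biased. The estimated indirect effect is the product of the two coefficients, so a genuine drop in PSS multiplied by a biased β gives a non-zero indirect effect that is not mediation.

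The plan reads a fall in ω causally. At stake is a conclusion that DHA improves temperament by reducing maternal stress, when DHA may have acted on temperament by another route and lowered stress separately. The bootstrapped intervals do not help, because they describe sampling error and not this bias. Baseline PSS carries much of the same tendency and cannot have been changed by the supplement, so its absence from the named covariates matters.

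**Working it through.** **1. Inputs from the document.**
- Analysed sample 108 and 54, two-sided 0.05 (power sections).
- PSS 27.5 (SD 3.4) vs 29.3 (SD 3.1) (power for Hypothesis 1). Pooled SD = √[(107×3.4² + 53×3.1²)/160] = 3.30. Effect = 1.8/3.30 = 0.545 SD.
- ICQ difference 3.7, SD 7.8 (power for Hypothesis 2). Effect = 3.7/7.8 = 0.474 SD. This is the difference detectable with 80% power, not an expected effect.

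**2. The plan's own power figures reproduce.** Noncentrality = effect × √(108×54/162) = effect × 6.
- ICQ: 0.474×6 = 2.85, power 80.8% (stated: 80%).
- PSS: 0.545×6 = 3.27, power 90.1% (stated: above 90%).

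**3. Assumptions; the document gives no figures.**
- Correlation between PSS and temperament due only to shared reporting: s = 0.1, 0.2 or 0.3.
- Correlation between a mother's self-reports on different occasions or scales: r = 0.5 to 0.7.
- True effect of stress on temperament: zero.

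**4. Size of the bias.** If k further self-reports are in the model, each correlated s with temperament and r with one another and with final PSS, symmetry gives β = s/(1 + k·r). The share of the treatment effect wrongly assigned to stress is 0.545×β/0.474 = 1.149×β.

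| Covariates (r = 0.5) | β | s = 0.1 | s = 0.2 | s = 0.3 |
|---|---|---|---|---|
| None (k = 0) | s | 11.5% | 23.0% | 34.5% |
| Baseline PSS (k = 1) | s/1.5 | 7.7% | 15.3% | 23.0% |
| Postpartum stress, depression, anxiety (k = 3) | s/2.5 | 4.6% | 9.2% | 13.8% |

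**5. How often mediation is falsely declared.** These rates come from simulated trials of 162 women with a latent reporting trait in all maternal questionnaires. Mediation is declared when the supplement-to-PSS and PSS-to-temperament coefficients both have p<0.05. Ranges cover r = 0.5 to 0.7.

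| Setting | s = 0.1 | s = 0.2 | s = 0.3 |
|---|---|---|---|
| No covariates | 22% | 64% | 88% |
| Same, total effect also significant | 17% | 52% | 73% |
| Same, and both effects halved | 3% | 9% | 14% |
| Baseline PSS added | 9-11% | 18-31% | 38-61% |
| Postpartum self-reports as covariates | 5-6% | 7-11% | 12-22% |

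If DHA does not change PSS, or reporting is not shared (s = 0), the rate is about 5% or below.

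**6. Check with a percentile bootstrap** (1000 trials per setting, r = 0.5). Intervals excluded zero in 20/64/88% with no covariates, 15/32/62% with baseline PSS, 8/14/29% with the postpartum self-reports, and 8/10/18% with both. The ordering is the same.

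**The case against.** **Can reporting style alone produce the finding?** A reader might infer this. The document does not support it: allocation is random and double-blind, so style cannot differ systematically between groups. Without a real effect on PSS the expected indirect effect is zero, as the rates of about 5% or below show. This objection stands, and the point is therefore conditional on DHA lowering PSS. That is the case which Hypothesis 1 expects and for which the trial claims more than 90% power.

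**Are the no-covariate rates those of the plan?** A reader might take 22/64/88% as the plan's error rate. They are not. The model has covariates, and three of the examples are maternal self-reports, which in these simulations remove more of the bias than baseline PSS does. This also stands. But the examples are not a fixed set, and under Hypothesis 2 the same factors enter only if the groups differ significantly. They are also measured after treatment: if supplementation affects them, conditioning on them distorts the effect being decomposed. Baseline PSS has neither problem.

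**Are the inputs favourable to the concern?** Partly. The ICQ effect is a detectable difference, the reporting correlations have no source in the document, and the final prenatal PSS and the last infant visit are months apart, so only a stable tendency would link them. With halved effects and a required total effect, the rate falls to 3/9/14%.

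**Is the remedy already in the plan?** Hypothesis 3 already admits outcomes that the mother does not rate, stress reactivity as a mediator, and multiple mediators. Ranking outcomes, or relabelling this pairing as exploratory, would therefore be a preference and not the repair of a defect. What the plan lacks is the baseline covariate and any statement that the mother-rated pair must be read alongside the others.

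**Conclusion.** The concern holds in conditional form and for one pairing: perceived stress as mediator of ICQ or IBQ-R temperament. If DHA lowers PSS, shared maternal reporting can produce apparent partial mediation with no effect of stress on temperament, and the model as written does not name the pre-treatment measure that would reduce it. At the document's effect sizes and an assumed shared-reporting correlation of 0.2, about 23% of the treatment effect would be wrongly assigned to stress without covariates, and about 15% with baseline PSS (r = 0.5). False declarations range from single figures to 88% according to the assumed correlation, the effect sizes and the covariates used. These percentages show direction and range; they are not an estimate for this trial.

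The randomised comparisons under Hypotheses 1 and 2 are not affected. Where the treatment variable is average blood DHA instead of assigned group, which the model also allows, the protection of the first path by randomisation is lost as well.

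**What to change.** In Hypothesis 3:

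1. When PSS is the mediator, always include baseline PSS in Z_i and in the supplement-to-PSS regression.
2. Do not rely on postpartum self-reports to deal with shared reporting, because they are measured after treatment.
3. Because baseline PSS is only a partial remedy, report PSS mediation of ICQ/IBQ-R next to the same mediation for infant outcomes not reported by the mother (NBAS, Bayley and its Behavior Ratings, infant cortisol). State that the mother reports both variables in the first analysis.
4. Do not conclude that stress mediates temperament from the mother-rated pair alone.

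The cost is a change of wording, one extra covariate that is already collected, and a more cautious conclusion for this one pairing. No new data or visits are needed.
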